7.2. Inclusion Criteria

To be eligible for this study, subjects must meet all of the following inclusion criteria.

1. Subjects must be willing and able to sign the informed consent and comply with the study protocol.
2. Must be ≥ 18 years of age.
3. Histologically confirmed metastatic melanoma with measurable (by RECIST v1.1), stage III (lymph node or in transit lesions) or stage IVA, IVB, or IVC disease that is accessible for injection. Stage should be determined using the American Joint Committee on Cancer (AJCC) Cancer Staging Manual, Seventh Edition ([Edge, 2010](#)).
4. Confirmed progression during or after treatment with a PD-1 inhibitor (cannot be part of bi-specific antibody) e.g. nivolumab or pembrolizumab. Confirmed progression is defined as:
 - Radiological progression (confirmed at least 4 weeks after the initial scan showing PD); or
 - For progression based solely on worsening of non-target or new, non-measurable disease, confirmation by an additional scan at least 4 weeks after the initial scan unless progression is accompanied by correlative symptoms.

In addition, all the following must hold:

- a) No intervening anti-cancer therapy between the last course of PD-1 inhibitor treatment and the first dose of study treatment is allowed except for local measures (e.g., surgical excision or biopsy, focal radiation therapy).
- b) The interval between last PD-1 inhibitor and start of study treatment should be at least 21 days with no residual anti-PD-1-related immune toxicities in excess of Grade 1 severity.
- c) Subjects who had adjuvant anti-PD-1 treatment are eligible if they have either disease recurrence after the end of adjuvant treatment or on-treatment disease recurrence after ≥ 12 weeks of adjuvant treatment.
- d) If subject BRAF mutation status is unknown, before randomization the subject must have BRAF testing performed using an approved assay method.

- e) Patients with BRAF-positive tumor(s) are eligible for the study if they received prior treatment with a BRAF inhibitor (alone or in combination with a MEK inhibitor) or declined targeted therapy.
5. ECOG Performance Status ≤ 1 .
6. Adequate baseline organ function as defined by:
 - a) Absolute neutrophil count (ANC) $\geq 1.5 \times 10^9/L$ (1500/mm³)
 - b) Platelet count $\geq 75 \times 10^9/L$ (75,000/mm³)
 - c) Hemoglobin ≥ 8.0 g/dL (4.96 mmol/L)
 - d) Serum creatinine ≤ 1.5 x upper limit of normal (ULN) or calculated creatinine clearance ≥ 60 mL/minute (\leq Grade 1)
 - e) Aspartate aminotransferase (AST) ≤ 2.5 x ULN; alanine aminotransferase (ALT) ≤ 2.5 x ULN; AST/ALT < 5 x ULN if liver involvement (\leq Grade 1)
 - f) Serum bilirubin ≤ 1.5 x ULN, except in subjects with Gilbert's Syndrome who must have a total bilirubin < 3 mg/dL (\leq Grade 1)
7. Women of childbearing potential (WOCBP) and men must agree to use effective contraceptive methods from screening until at least 90 days after the last dose of either ipilimumab or IMO-2125, whichever is later.

Non-childbearing potential is defined as a woman who meets *either* of the following criteria: a) postmenopausal state defined as no menses for 12 months without an alternative medical cause, or b) documented hysterectomy, bilateral tubal ligation, or bilateral oophorectomy.

Effective contraception methods are defined as *one* of the following:

- a) True abstinence, defined as refraining from heterosexual intercourse, when this is in line with the preferred and usual lifestyle of the subject. Periodic abstinence (e.g., calendar, ovulation, symptothermal, post-ovulation methods), declaration of abstinence for the duration of a trial, and withdrawal are not acceptable methods of contraception.
 - b) Condoms and spermicide
 - c) Diaphragm and spermicide
 - d) Oral or implanted hormonal contraceptive (e.g., Implanon™)
NOTE: For subjects in Sweden, low dose oral contraceptives are not permitted
 - e) An intra-uterine device
8. WOCBP must have a negative pregnancy test (serum or urine) according to the Schedule of Evaluations (Table 1 and Table 2).

7.3. Exclusion Criteria

Subjects meeting any of the following criteria will be excluded from the study:

1. Ocular melanoma.
2. Prior therapy with a TLR agonist, excluding topical agents.

3. Prior ipilimumab with the exception of adjuvant treatment completed ≥ 6 months prior to enrollment.
4. Systemic treatment with IFN- α within the previous 6 months.
5. Known hypersensitivity to any oligodeoxynucleotide.
6. Active autoimmune disease requiring disease-modifying therapy at the time of screening.
7. Subjects with a requirement for receiving more than physiologic doses of systemic steroids (>10 mg/day of prednisone or equivalent) for the 2 weeks preceding start of study treatment.
8. Subjects with another primary malignancy that has not been in remission for at least 3 years with the exception of non-melanoma skin cancer, curatively treated localized prostate cancer with non-detectable prostate-specific antigen, cervical carcinoma in situ on biopsy or a squamous intraepithelial lesion on Papanicolaou (Pap) smear, and thyroid cancer (except anaplastic).
9. Active systemic infections requiring antibiotics.
10. Known active, hepatitis A, B, or C infection.
11. Known diagnosis of human immunodeficiency virus (HIV) infection.
12. Women who are pregnant or breast-feeding.
13. Prior anaphylactic or other severe infusion reaction associated with human antibody administration that cannot be managed with standard supportive measures.
14. Presence of known central nervous system, meningeal, or epidural metastatic disease. However, subjects with known brain metastases are allowed if the brain metastases are stable for ≥ 4 weeks before the first dose of study treatment. Stable is defined as neurological symptoms not present or resolved to baseline, no radiologic evidence of progression, and steroid requirement of prednisone ≤ 10 mg/day or equivalent.
15. Impaired cardiac function or clinically significant cardiac disease.

8. STUDY DESIGN

8.1. Overview

This is a randomized Phase 3 global, multi-center, open-label comparison of ipilimumab with and without intratumoral IMO-2125 in subjects with advanced melanoma who had disease progression while on PD-1 directed therapy. Confirmed progression is defined by irRECIST criteria (see Section 20.3). Subjects will be randomized 1:1 to Arm A or B. Randomization is stratified on the duration of prior anti-PD-1 therapy (≥ 12 weeks vs < 12 weeks), metastasis stage (M1c vs other), and BRAF mutation status and prior targeted therapy (BRAF wild type, BRAF mutation positive with prior targeted therapy, or BRAF mutation positive with no prior targeted therapy) using block randomization. Targeted therapy is the use of an approved BRAF or MEK inhibitor alone or in combination. The primary endpoint family of the study comprises OS and ORR.

8.1.1. Independent Review Facility

Blinded independent review of all clinical and imaging results for response assessment will be performed centrally. The composition and duties of the blinded, independent reviewers are described in a separate charter.

8.1.2. Independent Data Monitoring Committee

The Independent Data Monitoring Committee (IDMC) composition and duties are described in a separate charter. Periodic data reviews will be performed by an IDMC as described in the IDMC Charter. The first IDMC meeting will occur after approximately 20 subjects on each arm have been treated with two doses of ipilimumab, and subsequent meetings occurring at regular intervals after the initial meeting until the database lock for the final analysis of OS. The initial meeting will review safety only. The IDMC will assess benefit:risk on an ongoing basis and will recommend early stopping if the safety profile is not acceptable given the efficacy of the study treatment.

8.2. Duration of Study

8.2.1. Treatment Duration

The Treatment Phase of the study is 10 weeks for subjects assigned to Arm A and 24 weeks for subjects assigned to Arm B.

8.2.2. Study Duration

The study is complete and final analysis will occur when approximately 392 randomized subjects have died, or approximately 36 months after the last subject is randomized, whichever occurs first; it is assumed this will take approximately 56 months after the first subject is randomized.

8.3. Study Drug Discontinuation and Study Withdrawal

8.3.1. Subject Discontinuation of Study Drug

Failure to complete Week 10 of study drug (Arm A) or Week 24 (Arm B) for any reason will be considered premature study drug discontinuation. Reasons for premature study drug discontinuation include PD (by irRECIST or by clinical progression), death, intolerable AE, withdrawal of consent, lost to follow up, Investigator discretion, Sponsor decision, and premature termination of the study.

Subjects who discontinue treatment prematurely prior to progression should continue to be followed according to the SOE (Active Follow-up). The Investigator will document the date of and reason(s) for study treatment discontinuation on the electronic case report form (eCRF). Once a subject discontinues study treatment permanently, they will not be able to be retreated.

Subjects who complete the planned study treatment and who have not progressed or started new anti-cancer therapy will enter the Active Follow-up Period and be followed according to the SOE. Subjects will enter the Survival Follow-up Period at disease progression or the start of new anti-cancer therapy (with or without disease progression).

8.3.2. Subject Withdrawal from the Study

Subjects are free to withdraw consent from participation in the study at any time. For any subject who withdraws consent due to an AE, the Investigator should arrange for the subject to be followed appropriately until the AE has resolved or stabilized (in the opinion of the Investigator).

The Investigator will document the reason(s) for study withdrawal on the eCRF. Idera and the Contract Research Organization (CRO) Medical Monitor should be informed when a subject is withdrawn from the study.

8.3.3. Study and Subject Completion

The study is complete when approximately 392 randomized subjects have died or approximately 36 months after the last subject is randomized, whichever occurs first.

A subject has completed the study at death. Subjects who withdraw from the study (including withdrawal of consent for study participation, lost to follow-up, premature termination of the study, or withdrawal at the discretion of the Investigator) will not be considered to have completed the study.

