Severe systemic reaction for which more aggressive measures including hospitalization are required (e.g., severe hypotension)	Supportive measures as required. Hold further dosing until the event resolves to baseline or G1 and the re-treatment criteria below are met.	None

Life-threatening AE (e.g., anaphylaxis)	Supportive measures as required.	Discontinue treatment
Serious procedural complication related to deep or visceral injection (e.g. pneumothorax or hematoma formation)	Supportive measures as required	Discontinue visceral injections (treatment may be continued if a superficial lesion or tumor-involved lymph node is available for injection instead)

Conventional supportive medications (including infliximab for immune-related colitis and growth factor support) are permitted.

Criteria for re-initiation of treatment with each dose of study drug include:

- ANC $\geq 1.5 \times 10^9/L$ (1500/ μL);
- Platelets $\geq 75 \times 10^9/L$ (75,000/ μL);
- Resolution of all clinically significant non-hematologic toxicities for which a causal association to study treatment cannot be ruled out to Grade ≤ 1 or baseline

Duration of study:

The Treatment Phase of the study is 10 weeks for subjects assigned to Arm A and 24 weeks for subjects assigned to Arm B. Subjects who discontinue disease assessments due to disease progression or the start of new anticancer treatment (with or without disease progression), will enter the Survival Follow-up Period (in which they are contacted by telephone according to the Schedule of Evaluations). Subjects who complete or discontinue study treatment for reasons other than disease progression or the start of new anticancer treatment but remain in the study will continue clinical and radiological disease evaluations in the Active Follow-up Period according to the Schedule of Evaluations.

The planned end of study will be approximately 56 months (the projected time for the required number of deaths to support the analysis of OS to occur) after the first subject is randomized.

Endpoints

Primary Endpoint Family:

The primary endpoint family (see Food and Drug Administration [FDA] Guidance for Industry, 2017) includes:

- ORR by blinded independent review using RECIST v1.1
- OS, defined as the time to death from any cause measured from the date of randomization

Secondary:

- ORR by investigator assessment using RECIST v1.1

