15.4.1.2. Primary Analysis of Overall Survival

Overall survival, defined as the time in months from randomization to death from any cause, will be analyzed using the Kaplan-Meier method after approximately 392 deaths have occurred, or approximately 36 months after the last subject is randomized, whichever occurs first. Sensitivity analyses will be detailed in the SAP.

The study hypotheses will be tested using a one-sided, stratified log-rank test. If the null hypothesis is rejected at the appropriate alpha level in accordance with the fallback method, it will be concluded that OS in the IMO-2125 + ipilimumab combination arm is statistically significantly superior to the OS in the ipilimumab alone arm.

Stratification factors will include duration of prior anti-programmed death receptor-1 (PD-1) therapy (≥ 12 weeks vs < 12 weeks), metastasis stage (M1c vs other), and BRAF mutation status and prior targeted therapy (BRAF wild type, BRAF mutation positive with prior targeted therapy, or BRAF mutation positive with no prior targeted therapy) using block randomization. Targeted therapy is the use of an approved BRAF or MEK inhibitor alone or in combination. Stratification will use block randomization. Depending on the distribution of the strata with the ITT, strata may be collapsed as appropriate. The full details will be specified within the SAP.

Subjects who have not died or who are lost to follow up at the data cut-off date will be censored at the last date they were known to be alive.

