#### **10.1.5 Sensitivity Analysis of Overall Survival using Imputed Death Dates**

As up to 10% of the enrolled subjects are anticipated to withdraw from the study early, a sensitivity analysis of OS will be performed where the missing death dates are imputed as the last known alive date +1 for the early withdrawn subjects. Results will be summarized with median, first, and third quartiles of Kaplan-Meier estimates with corresponding 95% CIs calculated by the Brookmeyer-Crowley method with log-log transformation. The HR and a 95% CI will be estimated using a Cox proportional hazards model, stratified by the same strata used in the analysis of ORR.

The following summary will be provided:

- Overall Survival Using Imputed Death Dates

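### Protocol 8.3.3 lists investigator discretion as a way to leave the study, with no provision for survival contact afterwards, so OS can be censored avoidably and perhaps informatively

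*Protocol*

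**What the plan says.** Investigator discretion appears twice in the Protocol, with different consequences.

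- **Stopping study drug (8.3.1).** The listed reasons include "Investigator discretion, Sponsor decision, and premature termination of the study". Follow-up then continues: "Subjects who discontinue treatment prematurely prior to progression should continue to be followed according to the SOE (Active Follow-up"). Subjects who progress or start another anticancer therapy move to Survival Follow-up, a telephone call every 3 months.
- **Leaving the study (8.3.3).** Beside withdrawn consent and loss to follow-up, the list of study withdrawals names "premature termination of the study, or withdrawal at the discretion of the Investigator) will not be considered to have completed the study".

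Protocol 8.3.2, the section on withdrawal from the study, describes withdrawal of consent. It requires the reason to be recorded on the eCRF and says the sponsor and the CRO Medical Monitor should be told. It sets no criteria for an investigator-initiated withdrawal, asks for no approval, and does not mention vital status afterwards.

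For the OS analysis, Protocol 15.4.1.2 says that subjects not known to have died "will be censored at the last date they were known to be alive". SAP 10.1.5 adds a sensitivity analysis: "As up to 10% of the enrolled subjects are anticipated to withdraw from the study early", so early withdrawals are counted as deaths on the day after they were last known alive.

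**The concern.** A subject whom the investigator takes out of the study has not refused contact. If the survival calls end there, a death that could have been recorded becomes a censored time.

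The trial is open-label, so the person making the decision knows the arm and the clinical course. The log-rank test and the Cox model assume that censoring tells nothing about the remaining survival time. Withdrawals that cluster shortly before death, and do so more in one arm, break that assumption and favour that arm. OS is the last test in the primary endpoint family, at one-sided 0.025 or 0.005 depending on the ORR result. Since survival follow-up is only a quarterly call, little is gained by ending it.

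**Working it through.** **1. Does OS follow-up stop?** No sentence says so outright. It follows from these provisions taken together:

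- Protocol Synopsis (Duration of study): Active Follow-up is for subjects who have stopped or completed treatment "but remain in the study will continue clinical and radiological disease evaluations in the Active Follow-up Period".
- Protocol 8.3.1 and footnote 4 of Tables 1 and 2: the way into Survival Follow-up is progression or new anticancer treatment. No route is given for a subject withdrawn from the study.
- SAP 9.1: end-of-study status is completed (death), ongoing or withdrawn, so a withdrawn subject is not ongoing.
- SAP 7: each subject's data enter the analysis sets up to completion, loss to follow-up or study withdrawal.
- Protocol 15.4.1.2: without a recorded death, OS is censored when the subject was last known alive.

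**2. The plan's own figure.** Inputs from Protocol 15.1 and SAP 4.5: HR 0.677, one-sided alpha 0.005, power 90%, 1:1 allocation. Schoenfeld's formula gives

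D = 4(z₀.₉₉₅ + z₀.₉₀)² / (ln 0.677)² = 4(2.576 + 1.282)² / 0.1522 ≈ 391.1, rounded up to **392**.

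This matches the plan. With 392 deaths, power is 0.901 at HR 0.677 (alpha 0.005) and 0.902 at HR 0.72 (alpha 0.025).

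**3. Non-differential loss.** Power = Φ(√D·|ln HR|/2 − z₁₋α). Losing 5% of 454, about 23 deaths, leaves 369 if the 36-month limit comes first. Power is then 0.879 (HR 0.677, alpha 0.005) and 0.884 (HR 0.72, alpha 0.025). If 392 deaths are still reached, the analysis is only later.

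**4. Informative loss in one arm.** Simulation with no treatment effect: 227 per arm, median 11.4 months in both arms, 20 months of uniform accrual, 10% background drop-out, analysis at 392 deaths or month 56, log-rank test, 6,000 runs per scenario. Assumed: a share of Arm B only is censored one month before death. Ranges show the spread between repeat runs.

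| Arm B withdrawn | Subjects (× 227) | HR | Error at 0.025 | Error at 0.005 |
|---|---|---|---|---|
| 0% | 0 | 1.00 | 2.5% | 0.5–0.7% |
| 2% | about 5 | 0.98 | 3.6–3.7% | 0.6–0.8% |
| 5% | about 11 | 0.95 | 6.2–7.2% | 1.7–1.9% |
| 8% | about 18 | 0.92–0.93 | 11.8–12.2% | 3.5–4.0% |

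The Monte Carlo standard error is √(0.005 × 0.995 / 6000) ≈ 0.09 percentage points at the 0.005 level, so the 2% row cannot be told apart from no withdrawal there. The exact lead time matters little: censoring 2 months before death, without background drop-out, gives errors of 3.9% and 0.9% at 2% withdrawn, and 6.9% and 1.5% at 5%.

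**5. Variants of the same simulation.**

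- 5% withdrawn in both arms: HR 1.00, errors about 2.8% and 0.5%. No bias.
- 5% withdrawn in Arm A only, true HR 0.72: power at 0.025 falls from 90% to about 78%.
- SAP 10.1.5 imputation applied to 2%, 5% and 8% withdrawn in Arm B: HR 1.00 each time. Errors are 2.8%, 2.2% and 2.3% at 0.025, and 0.6%, 0.4% and 0.4% at 0.005.

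**The case against.** The strongest reply has three parts.

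**The text is a definition.** Protocol 8.3.3 says who has not completed the study; it does not order an end to calls. The schedule footnotes run Survival Follow-up to death or the end of the study, and 8.3.4 treats a subject as lost only when it cannot be established whether death has occurred. This stands. A reader might infer that the protocol stops survival calls after an investigator withdrawal, and it does not say that. But nothing provides for the calls to continue either, and the provisions in step 1 point the other way. If continued contact is intended, the same edit makes it explicit.

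**The safeguards are real.** Withdrawal reasons go on the eCRF and are summarized and listed (SAP 9.1), so an imbalance between arms would be visible. In the scenario above, SAP 10.1.5 brings the hazard ratio back to 1.00. So it would be wrong to infer that 10.1.5 is of no use. Its limits are that it specifies quartiles and a hazard ratio with a confidence interval but no test, does not single out investigator withdrawals, and counts long survivors as deaths. The claim still rests on the primary test.

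**The error rates are a worst case.** They need withdrawals in one arm only, timed just before death. The documents give neither a rate nor any sign of that pattern, and balanced withdrawal gives no bias. This also stands: the table is an illustration, not a forecast.

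**Conclusion.** The point holds as an avoidable weakness in the wording of follow-up, not as a demonstrated bias. Protocol 8.3.3 makes investigator discretion a form of study withdrawal, and the documents imply, without stating it, that OS is then censored. The resulting loss could be informative, because the trial is open-label and the subject has not refused contact.

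The size depends wholly on an assumed withdrawal pattern. Under one-arm withdrawal of 2%, 5% or 8% one month before death, one-sided error at the 0.025 level is about 3.6%, 7% or 12%. At the 0.005 level the 5% and 8% cases give about 1.9% and 3.5%. A reader might infer that the planned OS test has inflated type I error; the documents do not support that, since they show no such pattern. The case for changing the wording is that vital status which could have been collected cannot be replaced by analysis later, and collecting it costs little.

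**What to change.** - In Protocol 8.3.3, delete investigator discretion from the list of study withdrawals. State in 8.3.2 and 8.3.3 that it can end study drug or study visits only, and that the subject then enters Survival Follow-up.
- In 8.3.2, separate stopping treatment, stopping visits and scans, and refusing survival contact.
- State that OS follow-up ends only at death, loss to follow-up, study completion or termination, or the subject's refusal of survival contact. Allow vital status to be taken from public records where consent and local law permit.

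The 454 subjects, 392 deaths and alpha allocation are unchanged, and no dosing or treatment-stopping rule is altered.

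The cost is a few more quarterly calls, one eCRF option, and the amendment submission and approvals described in Protocol 18.4. Searches of public records may also raise consent and data-protection questions under 18.2 and 18.3.

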8.3.4. Lost to Follow-up

Subjects are considered lost to follow-up if they cannot be contacted after at least 3 attempts over a 6-month period and it cannot be determined whether death has occurred.

